14.2 Criteria for un-blinding

Un-blinding on a subject level can be performed at any time if deemed necessary by the clinicians taking care of the patient. Un-blinding the clinical study as a whole requires major differences in the main outcome either at the interim-analysis on one-year data, or in the final results. Un-blinding the clinical study also requires agreement in the TSC to do this.

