5.1.4 Methodology

Data will be collected prior to the operation and at six weeks, one year, two years and five years after the operation. Clinical data, and answers to the PRO questionnaires will be collected and entered into the local register at these points except at six weeks where only data on complications will be entered. Data completeness at each time point will be assessed continuously at each hospital. Interim analysis will be performed every six month for 30 day complications, and every 12 months for primary endpoints.

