7.6 Provision for interim analyses

Interim analysis will be performed for complications by the DMC. Complications will be evaluated and compared between the two groups based on 30 day morbidity rates by data extraction and analysis every sixth month.

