13.6 Data monitoring committee (DMC)

Members and terms of reference:

The DMC will have three members: Two experts (one surgeon and one medical gastroenterologist) with a special knowledge of LSG and reflux, and one statistician. The DMC shall:

- 1. Monitor the data from the trial and make recommendations to the TSC (following each DMC meeting) on whether there are any ethical or safety reasons why the trial should not continue.
- 2. Ensure that the safety, rights and well-being of the trial participants is given highest priority.
- 3. Determine if additional interim analysis of trial data should be undertaken.
- 4. Consider the data from interim analyses, unblinded if considered appropriate, plus any additional safety issues for the trial and relevant information from other sources.
- 5. Consider any requests for release of interim trial data and to recommend to the TSC on the advisability of this.
- 6. The DMC may be asked by the TSC to consider data emerging from other related studies.

	RESEARCH PROTOCOL
Version no 4.0	Clinical intervention study

DMC meetings:

The DMC shall meet every six months, or more often if deemed necessary. Meetings will be called for and organized by the Principal Investigator of the trial in association with the Chairperson of the DMC. Dates for DMC meetings should be agreed in advance, and only altered with agreement of all members. All significant communications between the Principal Investigator and the DMC shall be in writing, or if they have to be verbal, they should be backed up by written records.

The role of the DMC is to look at the (unblinded) data from an ethical standpoint, the safety rights and wellbeing of the participants being paramount. The DMC is the only body involved in the trial that has access to the unblinded comparative data.

DMC Processes

The Principal Investigator should prepare a comprehensive report for the DMC. This should be prepared and circulated well in advance of the meeting to allow DMC members time to study the data. The content of the report should be agreed in advance with the DMC Chairperson. The trial statistician may be invited by the Chairperson to attend part of the meeting to present the data; otherwise, no one involved with the trial or TSC should be present to see the unblinded data.

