14 SUSPENSION OR PREMATURE TERMINATION OF THE CLINICAL STUDY

14.1 Criteria for suspension of the whole clinical study or in one or more sites

Potentially clinical relevant deviation in the number of serious events between the two groups (LSG – LSGG) will be discussed in the bi-annual meetings in the DMC. Similarly, interimanalysis will be performed on one-year follow-up data, and if differences in main outcome is found this will be addressed by the DMC. If the deviation is at one or a few sites only, these hospitals will be suspended until an explanation has been found. The steering committee will then decide whether or not to allow re-entry of this/these hospitals.

The study may be terminated by the representative for the research responsible institution or the investigator at any time. However, scheduled follow-up, as described in paragraph 6.6.4 and 6.6.5 should be continued for all subjects who were treated prior to termination of the study.

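### Section 14.2 allows whole-study un-blinding on an undefined major difference at the one-year look, before the two-year primary endpoint is recorded, and gives no route after a small or null final difference

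*Protocol*

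**What the plan says.** Section 14.2 has two separate rules. For the single patient: "Un-blinding on a subject level can be performed at any time if deemed necessary by the clinicians taking care of the patient". For the trial as a whole: "Un-blinding the clinical study as a whole requires major differences in the main outcome either at the interim-analysis on one-year data", with the final results as the alternative occasion. A further condition follows: "Un-blinding the clinical study also requires agreement in the TSC to do this". The section gives no other route and no threshold for a major difference.

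The one-year look comes from section 14.1: "interimanalysis will be performed on one-year follow-up data, and if differences in main outcome is found this will be addressed by the DMC". Section 5.1.4 schedules interim analyses "every 12 months for primary endpoints". The interim provision in the statistics chapter, section 7.6, mentions safety only: "Interim analysis will be performed for complications by the DMC".

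Four other statements bear on the rule:

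- **Endpoint.** The summary and section 6.6.4 define the primary outcome as continuous ARM use for reflux at two years, or reoperation for reflux disease within two years.
- **One-year data.** Section 6.6.4 says these will not be published separately, partly because ARM use goes on rising between the first and second year.
- **Blinding.** Sections 4 and 5.1.1 call the trial triple-blind. Section 13.6 adds: "The DMC is the only body involved in the trial that has access to the unblinded comparative data".
- **Reporting.** Section 15 commits to submitting the results for publication at completion, without any condition on what they show.

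**The concern.** The rule ties opening the blind to the size of the observed effect, and it allows this one year before a patient's primary endpoint is due. Had the endpoint been a laboratory value, this might matter little. Here it is daily medication use. Section 6.6.3 itself names differences in prescribing culture and in patients' demand for ARM as threats to interpretation. It asks that the reason for ARM use be addressed at the one-, two- and five-year visits, and appendix 17.4 has clinicians consider at each follow-up whether it can be stopped. Anyone who knows both the allocation and a favourable one-year result could be influenced in those conversations, and the two-year comparison could then drift towards the one-year finding.

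The second problem lies at the end of the trial. A major difference is worded as a requirement and covers the final results too. A trial that ends with a small or null difference does not meet it.

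**Working it through.** **1. The plan's own sample size.** This is checked only to show that it is not in question. Inputs from sections 7.2 to 7.4: 14% v 7%, alpha 5% (taken as two-sided), power 85%, drop-out 20%.

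n per arm = [1.960·√(2·0.105·0.895) + 1.036·√(0.14·0.86 + 0.07·0.93)]² / 0.07² ≈ 343, so 686 in total. Then 686 / 0.80 = 857.5, rounded up to 858, and 900 are planned. All three figures stand.

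**2. Who would still lack the primary endpoint at a one-year look?** Inputs: 900 patients (section 6.5.7) and an inclusion period of two years (section 6.5.5). Uniform accrual is an assumption. The rate is 900 / 24 = 37.5 patients per month. At month t from study start, with each bracket limited to the range 0 to 24:

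- randomised = 37.5 × [t]
- reached one year = 37.5 × [t − 12]
- reached two years = 37.5 × [t − 24]

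| Month | Randomised | Reached one year | Reached two years | Of 900, not yet at two years |
|---|---|---|---|---|
| 12 | 450 | 0 | 0 | 900 |
| 24 | 900 | 450 | 0 | 900 |
| 30 | 900 | 675 | 225 | 675 |
| 36 | 900 | 900 | 450 | 450 |
| 48 | 900 | 900 | 900 | 0 |

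If the 12-monthly looks are counted from study start, month 24 is the first with any one-year data. Month 36 is when the last patient reaches one year. Whole-study un-blinding on one-year data between those dates would leave from 900/900 = 100% down to 450/900 = 50% of patients with an open allocation before their primary assessment. The planned 20% drop-out scales the counts (900 × 0.80 = 720 evaluable; 450 × 0.80 = 360) but not the percentages, if it is spread evenly over accrual.

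**3. What this could do to the result.** Suppose knowledge of allocation shifts the between-arm difference in ARM use by d percentage points among exposed patients. The overall difference then moves by f × d, with f between 0.5 and 1. The documents give no basis for a value of d, so the bias itself cannot be sized. Only the exposed share can.

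**4. The final-results limb.** Section 14.2 lists its conditions as requirements: (a) a major difference, at the one-year look or at the end, and (b) TSC agreement. If (a) fails at both times, nothing else in the section allows whole-study un-blinding. Section 15 expects publication in every case. The two sections do not formally exclude each other, but 14.2 does not describe how a null trial reaches an un-blinded report.

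**The case against.** The best defence is context. Section 14.2 sits in the chapter on suspension and early termination, directly after a section in which one-year differences go to the DMC. Section 13.6 foresees DMC advice that may lead the TSC to stop for a clear outcome. On that reading, one-year un-blinding simply belongs to DMC-led stopping, and since TSC agreement is needed it may never happen. The second part stands: the break is permitted, not planned. The first is plausible, but 14.2 does not say it. Moreover, section 14.1 continues scheduled follow-up after termination, so two-year outcomes would still be collected.

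Several stronger readings are tempting and are not supported:

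- **Built-in reporting bias.** A reader might infer that a null trial would stay unreported. Section 15 commits to publication without condition. Allocation lists go to the Norwegian register (SOReg-N) every month (sections 5.1.5, 6.6.2 and 7.1), and section 13.5 places the trial statistician there. The comparison by allocated group can therefore be run and published. This limb looks like loose drafting rather than intent.
- **A direct conflict with section 13.6.** A reader might infer that the TSC must see comparative data in order to agree. Section 13.6 lets the DMC advise the TSC in writing, including on requests to release interim data, so the TSC can act on advice alone.
- **ARM stopped at every visit under section 6.6.3.** That section asks for ARM without an obvious reason to be stopped only at the first follow-up. At later visits the reason is to be addressed. The wider prompt is in appendix 17.4, and it asks for an evaluation.
- **A probability that no route exists.** One could quote the chance of a non-significant result, but that equates a major difference with statistical significance, which the protocol does not do.

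**Conclusion.** The point holds in limited form. As written, section 14.2 permits the whole study to be un-blinded on an undefined major difference at a one-year look, when about 450 (month 36) to all 900 (month 24) patients have yet to provide the two-year primary endpoint. These counts rest on uniform accrual over the planned two years. The concern about bias rests on ARM use being open to patient and prescriber behaviour, which the protocol itself acknowledges. The size of any bias is unknown, and an early break needs TSC agreement.

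The final-results limb is a lesser defect: read literally it leaves a small or null result without an un-blinding route, although nothing prevents such a result from being analysed and reported. The sample size is unaffected. The rule should be reworded, because following it as it stands could damage the primary comparison.

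**What to change.** Replace the whole-study rule in section 14.2 with text to this effect:

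> The study team is un-blinded once, after the two-year database has been locked, whatever the result. Comparative one-year results remain within the DMC. No whole-study un-blinding follows a one-year look unless the trial is stopped on DMC advice.

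Leave the subject-level rule for clinical need unchanged. Keeping patients and follow-up clinicians masked until the five-year visit would also protect the later assessments, but it is optional: the defect does not require it, and patients would wait longer to learn their allocation.

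The cost is one paragraph, passed through the amendment route in section 9 (TSC agreement and ethics approval). Sample size, visits and data collection do not change.

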14.3 Requirements for subject follow-up

The project leader will be the person in charge from the research responsible institution. Subject follow-up will be surveilled by the local representative for the study in each participating hospital. In general, patient follow-up will be the same independently of whether a patient is included in the study or not. If necessary, the local representative will contact the national coordinator or the project leader if any queries concerning follow-up of a particular patient.

15 PUBLICATION POLICY

The study will be registered at ClinicalTrials.gov before starting.

Upon study completion, the results of this study will be submitted for publication in peer-reviewed journals.

A summary of the study findings will be submitted to the Ethics Committee according to national regulations in Norway.

All personnel who have contributed significantly with the planning and performance of the study (Vancouver convention 1988) may be included in the list of authors.

17 APPENDICES

17.1 Surgical technique

Laparoscopic sleeve gastrectomy with gastropexy (supplementary to the video).

The greater curvature has been mobilized from the pylorus to the left crus. The hiatus is briefly explored and in this patient the hiatal opening does not seem enlarged. If enlarged¹, a crural

	RESEARCH PROTOCOL
Version no 4.0	Clinical intervention study

repair should be done if possible, leaving the diaphragmatic opening about the size of the oesophagus.

A 32 french tube is passed into the stomach and down to the pylorus. Torsion of the stomach while stapling is avoided.

The resection is started 1-2 cm from the pylorus. This surgeon prefers to use a black cartridge on the antrum to avoid cracks in the serosa. The resection at this part is performed loosely along the 32 french tube.

Above the incisura angularis the stapler is closer to the 32 fr tube.

The resection continues in a straight line along the tube, and ends one cm lateral to the gastro-oesophageal junction. Whether to staple through the fat pad like here, or remove parts of the fat pad in order to better visualize the gastro-oesophageal junction can be decided by the operating surgeon.

The gastric tube is removed.

Whether the upper end of the staple line is oversewn, inverted or reinforced by other means is decided by the operating surgeon. In this case no suturing or reinforcement is used.

It is important that the gastropexy starts at the upper end of the staple line. A 2-0 non-absorbable suture like Etibond is used.

The gastro-splenic ligament is approached and sutured to the upper end of the staple line. It is important to catch a good bite of the gastro-splenic ligament, preferentially larger than shown here, in order to creat a cushion attempting to prevent the cardia from intrathoracic migration.

The second stitch is placed in a similar manner including a good bite of the gastro-splenic ligament. To avoid using a thinner and weaker part of the gastro-splenic ligament, and to avoid too much traction between the tissues, the surgeon here decides to go lateral to the resection-line on the gastrosplenic ligament.

If there is a dimple or kink in the staple line on the stomach, this can be lifted by the suture as shown here.

On the one hand the sutures should include good bites of the fatty ligament, while on the other hand a suture must not become too tight when approximating the tissues in order to avoid a pull-through of the fat or staple line. When pulling a suture in order to approximate tissues, the angle of traction must always be greater than 90 degrees on the staple line in order to avoid a possible cutting effect.

Further down, the gastroepiploic artery or arcade becomes visible, and the surgeon outlines the gastroepiploic arcade for us. This arcade should be included in the suture line in order to increase the support for the suture, reduce the risk of a pull-through and strengthen the force of downward traction on the gastric remnant.

Performing gastropexy on the antrum of the stomach might be somewhat more difficult because of the angulation for suturing if the "French position" is used, and some of you might want to suture backhand here. Standing on the patients right side could make this part of the suturing easier. The gastropexy is continued to well below the incisura angularis. Performing gastropexy on the last 3-4 centimetres of the staple line does probably not contribute to traction on the upper part of the gastric remnant and is therefore not a part of the study. It might however be performed based on the surgeons preference since it compresses the staple line and thereby potentially could reduce bleeding.

	RESEARCH PROTOCOL
Version no 4.0	Clinical intervention study

The end result of the gastropexy should be a gastric remnant without kinks and torsion, and with a continuous traction from the gastrosplenic and gastrocolic ligament in order to keep the gastro-oesophageal junction below the diaphragm.

If possible, crural repair should be performed if a hiatal hernia, a Hill grade IV and possibly also if a Hill grade III has been found either on the preoperative gastroscopy or during the operation, in accordance with the 1st international consensus conference on sleeve and reflux. The cardia is mobilized and a full hiatal dissection is performed. The gastro-oesophageal junction is brought into the abdomen. A posterior crural repair is performed with non-absorbable material using double sutures. In this case also an anterior crural suture is used in order to approximate the crura to the empty oesophagus.

1. Enlarged = Hill grad IV, and possibly Hill grade III (decided by the operating surgeon).

17.2 Gastroskopi

Standard gastroskopi for Sleeve pex studien.

Under nedføring av skopet, sjå etter øsofagitt eller anna patologi i øsofagus. Dersom synleg øsofagitt; klassifiser etter Los Angeles klassifikasjonen (grad A, B, C eller D).

Skopet førast til duodenum. På veg tilbake tek ein slimhinneprøver frå antrum og corpus for analyse på Helikobakter pylori (HP). Dersom pasienten brukar PPI tek ein ikkje slimhinneprøve men i staden feces-prøve (tilrådd), alternativt blodprøve eller pusteprøve.

I øvre del av magesekken retroflekterer ein skopet og vurderer diafragmaåpninga nedanfrå. Grader diafragmaåpninga etter Hill's gradering (grad I, II, III, IV). Preoperativt er dette uproblematisk, postoperativt etter sleeve er dette oftast umogeleg.

Mål avstanden tannrekka-diafragma, deretter avstanden tannrekka GØ-overgangen på veg ut.

Dersom eit funn er mistenkeleg på Barret's; estimer lengste utstrekning i breidde- og lengderetning i cm (Prague Circumferential and Maximal extent (CM) kriteria). Berre slimhinnetunger som er ≥ 1 cm over GØ-overgangen og inneheld intestinal metaplasia blir definert som Barret's.

Ved postoperative skopiar, noter konfigurasjonen på rest-magesekken: Pen form? Striktur? Vridning? Andre spesielle forhold? (Førast under «Andre funn» i gastroskopi-skjemaet til SOReg).

Dokumenter gjerne funn med foto eller video. Ta eventuelle biopsiar til slutt.

Referansar:

	RESEARCH PROTOCOL
Version no 4.0	Clinical intervention study

Sjå gastroskopi-skjemaet på SOReg si heimeside: Gastroskopi-skjema 2020.pdf (helsebergen.no)

English text:

Standard gastroscopy for the Sleeve Pex study.

When starting, look for oesophagitis or other pathology in the oesophagus. If oesophagitis is observed; classify according to the Los Angeles classification (grade A, B, C, D).

Pass the endoscope to the duodenum. When retracting the scope, take mucosal-samples from the antrum and body of the stomach in order to check for Helicobacter Pylori (HP). Do not take samples if the patient is using PPI; then use fecal test (advised), blood-test or breathing test.

Retroflect the scope in the upper part of the stomach and evaluate the diaphragmatic opening from below. Grade the opening according to Hill's grade (grad I, II, III, IV). Preoperatively this is easily performed, postoperatively this is often not possible after a sleeve gastrectomy.

Measure the distance from the teeth to the diaphragm, secondly the distance from the teeth to the GO-junction.

If an area is suspicious of Barret`s; estimate the longest and broadest area in cm (Prague Circumferential and Maximal extent (CM) criteria). Only mucosal tongues that extends ≥ 1 cm up from the GO-junction and have intestinal metaplasia are defined as Barret`s.

For postoperative endoscopies: Note the configuration of the gastric remnant. Smooth form? Stricture? Torsion? Other findings? (Findings can be noted under "other findings" in the gastroscopy-modul in SOReg).

Findings should be documented by a photo or video. If biopsies are taken, these should be taken at the end of the procedure.

17.3 Kontroll av operasjonsteknikk

Video for kontroll av operasjonsteknikk før inklusjon i Sleeve pex studien.

Før ein inkluderer pasientar til deltaking i studien må ein verifisere at det kirurgiske teamet utfører operasjonen i samsvar med protokoll. Dette gjer ein ved å utføre operasjonen med video-opptak av dei sentrale delane av operasjonen: Ventrikkelreseksjon og gastropexi.

For å kunne gjere video-opptak må pasienten vere informert om studien, om at det vert gjort opptak av operasjonen, og at videoen vil bli vurdert av styremedlemmer frå styrekomiteen for studien. Det må dokumenteras i pasienten sin journal at pasienten har fått slik informasjon.

Videoen skal vere anonym, dvs den skal ikkje innehalde bilete, tekst eller liknande som kan bidra til å identifisere pasienten. Den skal berre innehalde bilete frå innsida av abdomen. Den må vise ventrikkelreseksjonen og gastropexien uredigert. Formatet må vere slik at den kan avspelast på eit framvisingsprogram som er godkjent for bruk i helsevesenet.

Video sendast på kryptert minnepenn som brevpost til: Helse Bergen, SOReg-N v/[name], [name]. Videoen blir vurdert av medlemmer av styringskomiteen. Det kirurgiske teamet får tilbakemelding og minnepennen vert returnert.

	RESEARCH PROTOCOL
Version no 4.0	Clinical intervention study

English text:

Video to verify correct operation technique before including patients:

Before enrolling patients into the study, the surgical team at the individual hospital must verify that the operation is being performed according to the protocol. This is done by recording the most important parts of the operation: The gastric resection and the gastropexy.

Before recording, the patient must be informed about the study and the recording, and that the video will be evaluated by representatives for the steering committee of the study. It must be documented in the patient chart that the patient has received such information.

The video shall not contain pictures, text or other elements that can identify the patient. Only recordings from inside the abdomen must be used. The video must show the full gastric resection and gastropexy, and the format be must such that it can be shared in a safe way.

